8. STUDY ASSESSMENTS AND PROCEDURES

8.1. Administrative and General Procedures

8.1.1. Informed Consent Process

- The investigator or their representative will explain the nature of the study to the participant or their legally authorized representative and answer all questions regarding the study.
 - Informed consent must be obtained before any study-related procedures are conducted, unless otherwise specified by the Protocol.
 - Informed consent must be obtained using the IRB/IEC-approved version in a language that is native and understandable to the participant. An ICF template will be provided by the sponsor or its designee. The sponsor or its designee must review and acknowledge the site-specific changes to the ICF template. The ICF must include a statement that the sponsor or its designee and regulatory authorities have direct access to participant records.
 - The ICF must contain all required elements including optional samples/procedures (eg, optional biopsy) and describe the nature, scope, and possible consequences of the study in a form understandable to the study participant.
- Participants must be informed that their participation is voluntary. Participants or their legally authorized representative will be required to sign a statement of informed consent that meets the applicable requirements and regulations for the country(ies) in which the study is being conducted as well as the IRB/IEC or study center.
- The participant must be informed that their personal study-related data will be used by the sponsor in accordance with local data protection laws. The level of disclosure must also be explained to the participant.
- The participant must be informed that their medical records may be examined by Clinical Quality Assurance auditors or other authorized personnel appointed by the sponsor, by appropriate IRB/IEC members, and by inspectors from regulatory authorities.
- The medical record must include a statement that written informed consent was obtained before the participant was enrolled in the study and the date the written consent was obtained. The authorized person obtaining the informed consent must also sign the ICF.
- Participants must provide consent to the most current version of the ICF during their participation in the study.
- A copy of the ICF(s) must be provided to the participant or the participant's legally authorized representative.
- Participants who are rescreened are required to sign a new ICF and must be assigned a new participant ID number.

8.1.2. Screening Procedures

Screening is the interval between signing the ICF and the day the participant is enrolled in the study (Day 1). Screening may not exceed 28 days. Assessments that are required to demonstrate eligibility may be performed over the course of 1 or more days during the screening process.

Procedures conducted as part of the participant's routine clinical management (eg, blood counts or physical examinations) and obtained before signing of the ICF may be used for screening or baseline purposes provided that the procedure meets the Protocol-defined criteria and has been performed in the timeframe of the study (ie, within 28 days or less prior to Day 1). For participants who are enrolled in the study, information associated with eligibility requirements must be entered into the appropriate eCRF pages.

Results from the screening visit evaluations will be reviewed to confirm eligibility before randomization and the administration of study drug. Tests with results that fail eligibility requirements may be repeated once during screening if the investigator believes the results to be in error. For screening assessments that are repeated, the most recent available result before randomization will be used to determine eligibility.

See Sections 5.4 and 5.5 for information regarding screen failures and replacement of participants, respectively.

8.1.3. Interactive Response Technology Procedure

Each participant will be identified in the study by a participant ID number, which is a combination of a country's abbreviation, the site ID, and the participant ID number. Site staff should contact the IRT to obtain the participant ID number during screening. Upon determining that the participant is eligible for study entry, the IRT will be contacted to obtain the treatment assignment. Additionally, the IRT will be contacted at each regular study visit during both the DBVC period and the OLE period including unscheduled visits and safety follow-up visits (see Table 3) to update the study drug supply. Additional details are provided in the IRT Manual.

8.1.4. Distribution of Reminder Cards and/or Diaries

| Participants will be provided with a remind | der card at each visit. The reminder card will indicate |
|---|---|
| the date/time of the next visit and will also | remind the participant that they should not apply their |
| morning application of study drug on Wee | k 2 and Week 4 visit, as they will apply it after blood |
| draws for sa | afety evaluation have been completed. |

Participants will be instructed on the use of the drug application diary during the screening visit. Daily study drug administration will be recorded in the diary and verified by the study investigator/designee at study visits as shown in Table 3.

[figure not shown]
8.1.5. Demography and Medical History

8.1.5.1. Demographics and General Medical History

Demographic data and general medical history will be collected at screening by the investigator or qualified designee and will include year of birth/age, race, ethnicity, medical and surgical history, and current illnesses. Medical history will include relevant medical or surgical treatments within the last 2 years that are considered to be clinically significant by the investigator.

8.1.5.2. Disease Characteristics and Treatment History

Relevant medical and treatment history for the past year will be collected at screening by the investigator or qualified designee. Details regarding the participant's history of LS, including date of diagnosis, relevant disease characteristics, and prior treatments with outcome (eg, inadequate response) and reason for stopping treatment will be recorded.

8.2. Efficacy Assessments

8.2.1. Medical Resource Utilization and Health Economics

Medical resource utilization and health economics parameters are not evaluated in this study.

8.2.3. Clinical Lichen Sclerosus Score

The CLISSCO is a validated tool to assess disease severity in vulvar lichen sclerosus. Clinical Lichen Sclerosus Score consists of 12 items divided into 3 sections: (a) symptoms (3 items; likely reversible [ie, itch, pain, dysuria]), (b) signs (3 items; possibly reversible [ie, whitening, petechiae/ecchymosis, fissures]), and (c) architectural changes (6 items; irreversible [ie, skin fusion, perianal involvement, etc]). All symptoms, signs, and architectural changes will be rated on a 4-point Likert scale (0 = absent; 1 = mild; 2 = moderate; 3 = severe; Erni et al 2021). Investigator will be asked to document score of each of the 12 items based on schedule stipulated in SoA (see Table 3).

8.2.5. Body Surface Area

Total % BSA affected will be estimated at each visit as outlined in the SoA (see Table 3). Body surface area assessment will be approximated to the nearest 0.1% using the Palmar Method as a guide, which is the palm plus 5 digits, with fingers tucked together and thumb tucked to the side (handprint), as 1% BSA and the thumb as 0.1% BSA.

8.2.6. Photography

At select sites, photographs of the LS lesions will be taken at visits indicated in Table 3. Detailed methods for capturing photographs will be provided in the Study Manual.

8.2.7. Patient-Reported Outcomes

Patient-reported outcomes will be collected and assessed as outlined in the SoA (see Table 3). For all patient-reported outcome assessments conducted at the study site, in order to avoid bias in the participants' responses to the questionnaires, assessments should be completed before any other evaluations or study procedures on the day of the study visit and prior to treatment-related discussions with the investigator or study site staff.

8.2.7.1. Diary Assessments: Itch NRS and Skin Pain NRS

The participant will rate the following:

- Itch NRS: The Itch NRS is a daily participant-reported measure (24-hour recall) of the worst level of itch intensity (Kimball et al 2016, Silverberg et al 2021). The participant will be instructed to complete and record the Itch NRS via a diary, daily, in the evening beginning on the day of screening through Week 24 or treatment discontinuation. The participant will rate itch severity of their LS by selecting a number from 0 (no itch) to 10 (worst imaginable itch) that best describes the worst level of itching in the past 24 hours.
- Skin Pain NRS: Pain (includes all types of pain such as feeling of burning, tearing, pulling, stabbing, etc) severity of the LS by selecting a number from 0 (no pain) to 10 (worst imaginable pain) that best describes their worst level of pain in the past 24 hours. The participant will be instructed to complete and record the Pain NRS via a diary, daily, in the evening beginning on the day of screening through Week 24 or treatment discontinuation based on 24-hour recall.

The average of the 7-day Itch NRS score prior to the baseline visit (minimum 4 out of 7 days' data required) will be used to determine if a participant meets inclusion criteria.

In addition, the diary may be used for optional reporting of sexual activity or other activities, which may exacerbate pain or itching. Detailed directions for the administration of a diary will be provided in the Study Manual.

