| LS assessment under magnification* | X | X | X | X | X | X | X | X | X | | | *See Section 8.3.4.3. |
| Vital signs | X | X | X | X | X | X | X | X | X | X | X | |
| AE assessments | X | X | X | X | X | X | X | X | X | X | X | |
| Efficacy assessments | | | | | | | | | | | | |
| | | | | | | | | | | | | |
| CLISSCO | X | X | X | X | X | X | X | X | X | | | |
| | ı | | | | | | 1 | | 1 | 1 | | |
| %BSA* | X | X | X | X | X | X | X | X | Х | X | | *The total %BSA affected should be ≤ 10% to be eligible for study entry and continued participation. |
| Photography (selected sites only) | | X | | X | X | X | X | X | X | | | |

Table 3: Schedule of Activities (Continued)

| | | | | | | | | | | | Safety | |
|---------------------------|-----------|-----------|-----------|-------------|-------------|--------------|-----------|-----------|---------------------------------|----------------|----------------------------|--|
| | Screening | | | DBV | C Perio | | | OLE Pe | eriod ^a | | Follow-up | |
| | Days | Baseline | | | | | | | Wk 24 (EOT2)/ET ^b | | 30 Days (+ 7 Days After | |
| Visit Day (Range) | −28 to −1 | (Day 1) | (± 3 d) | $(\pm 3 d)$ | $(\pm 3 d)$ | (± 3 d) | (± 3 d) | (± 3 d) | (± 3 d) | Visit | Last Application) | Notes |
| Patient-reported outco | omes | | | | | | | | | | | |
| | | | | | | | | | | | | |
| Itch NRS | | Completed | l each ev | ening th | rough th | e last appli | cation of | study dru | ıg. | | | |
| Skin Pain NRS | | Completed | l each ev | ening th | rough th | e last appli | cation of | study dru | ıg. | | | |
| Laboratory assessmen | nts. | | | | | | | | | | | |
| | î . | X* | | 1 | 1 | X | | 1 | X | Χ [†] | X | *N-4 |
| Chemistry assessments | X | X | | | | X | | | X | Χ' | | *Not necessary if screening assessment is performed within 14 days of Day 1. |
| | | | | | | | | | | | | †Laboratory assessment are optional during unscheduled visits based on investigator's discretion and clinical judgment. |
| Hematology assessments | X | X* | | | | X | | | X | Χ [†] | | *Not necessary if screening assessment is performed within 14 days of Day 1. |
| | | | | | | | | | | | | †Laboratory assessment are optional during unscheduled visits based on investigator's discretion and clinical judgment. |

Table 3: Schedule of Activities (Continued)

| | Screening | | | DBV | C Period | Į | | OLE Pe | rioda | | Safety Follow-up | |

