| Visit Day (Range) | -28 to -1 | (Day 1) | (± 3 d) | $(\pm 3 d)$ | (± 3 d) | (± 3 d) | (± 3 d) | $(\pm 3 d)$ | $(\pm 3 d)$ | Visit | Last Application) | Notes |
| Biopsy (select sites only) | X* | | | | | | | | | | | *Screening biopsy from anogenital area to confirm diagnosis (to be performed locally) if no prior biopsy was done. If a biopsy is done to confirm the diagnosis of LS during screening period, screening period can be extended to 6 weeks to allow for histological examination. |

Table 3: Schedule of Activities (Continued)

| | Screening | | | DBVC | Period | | | OLE Pe | riod ^a | | Safety Follow-up | |
|-------------------|-----------|----------|-------------|-------------|-------------|---------------------|-------------|-------------|------------------------|-------------|-------------------------|-------|
| | | | | | | Wk 12a | | | Wk 24 | | 30 Days | |
| | Days | Baseline | | | | (EOT1) ^b | | | (EOT2)/ET ^b | Unscheduled | (+ 7 Days After Last | |
| Visit Day (Range) | −28 to −1 | (Day 1) | $(\pm 3 d)$ | $(\pm 3 d)$ | $(\pm 3 d)$ | $(\pm 3 d)$ | $(\pm 3 d)$ | $(\pm 3 d)$ | $(\pm 3 d)$ | Visit | Application) | Notes |
| | | | | | | | | | | | | |
| | | | | | | | | | | | | |

^a All Week 12 assessments must be completed before the participant can continue in the OLE.

b Assessment for ET will be the same as Week 24 visit. Early termination will be called ET1 during DBVC and ET2 during OLE.

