7. DISCONTINUATION OF STUDY TREATMENT AND PARTICIPANT WITHDRAWAL

7.1. Discontinuation of Study Treatment

7.1.1. Reasons for Discontinuation

Participants **must** be discontinued from study treatment for the following reasons:

- Disease worsens during either the DBVC period or the OLE period, to the point where the extent of affected area to be treated exceeds 10% BSA.
- Worsening LS and treatment with a prohibited medication as noted in Section 6.6.3.
- The participant becomes pregnant.
- Consent is withdrawn.

Note: Consent withdrawn means that the participant has explicitly indicated that they do not want to be followed any longer; in this case no further data, except data in public domain, may be collected on or solicited from the participant. Participants may choose to discontinue study treatment and remain in the study to be followed for safety/efficacy assessments.

- Further participation would be injurious to the participant's health or well-being, in the investigator's medical judgment.
- Unacceptable toxicity occurs (see Table 7).
- The study is terminated by the sponsor.
- The study is terminated by the local health authority, IRB, or IEC.

A participant **may** be discontinued from study treatment for the following reasons:

- If, after 2 consecutive study visits and reinforcement of study drug application by site staff, a participant's drug usage exceeds one 60-g tube every 4 days; a participant who again fails to meet compliance benchmarks at a subsequent visit may be considered for withdrawal from the study. The medical monitor should be consulted for instruction on handling the participant.
- If, during the course of the study, a participant is found not to have met eligibility criteria, the medical monitor, in collaboration with the investigator, will determine whether the participant should be withdrawn from study treatment.
- If a participant is noncompliant with study procedures or study drug application in the investigator's opinion, the sponsor should be consulted for instruction on handling the participant.

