7.1.2. Discontinuation Procedures

In the event that the decision is made to permanently discontinue the study treatment prior to the Week 12 (or Week 24) visit, the ET1 (or ET2) visit should be conducted. Reasonable efforts should be made to have the participant return for a follow-up visit. The last date of the last application of study cream and the reason for discontinuation of study cream will be recorded in the eCRF.

If a participant is discontinued from study treatment:

- The study monitor or sponsor must be notified.
- The reason(s) for discontinuation must be documented in the participant's medical record and the primary reason for discontinuation must be included in the eCRF.
- The ET visit should be performed, and the date recorded.
- The status of the participant should be updated to ET in the IRT system.
- Participants must be followed for safety until the time of the follow-up visit or until study drug-related toxicities resolve, return to baseline, or are deemed irreversible, whichever is longest.

If the participant discontinues study treatment and actively withdraws consent for collection of follow-up data (safety follow-up or disease assessment), then no additional data collection should occur; however, participants will have the option of withdrawing consent for study treatment but continuing in the follow-up period of the study for safety/efficacy assessments.

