7.2.5.2. Skin Pain Numerical Rating Scale

Participants will be instructed to complete and record the Skin Pain NRS in a diary each evening beginning on the day of screening through Week 24 or treatment discontinuation. Participants will rate their pain, which will include all types of pain (eg, burning, tearing, pulling, stabbing, etc) severity of the LS by selecting a number from 0 (no pain) to 10 (worst imaginable pain) that best describes the worst level of pain they experienced in the past 24 hours.

The participant's baseline Skin Pain NRS score will be determined by averaging the 7 daily NRS scores before Day 1 (ie, Days –7 to –1) for all the by-visit summaries. The by-visit Skin Pain NRS score for postbaseline visits will be determined by averaging the 7 daily NRS scores before the visit day. If 4 or more daily scores (out of the 7) are missing, the Skin Pain NRS score at the visit will be set to missing. For all daily skin pain-related analyses, baseline will be defined as the last available Skin Pain NRS score during the week prior to Day 1 (ie, Days –7 to –1). No imputation will be performed for missing values.

l
1
Ī
_

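### The Itch and Skin Pain NRS diary stops with the cream although women who stop may stay in the study for efficacy assessment, so their Week 12 scores are not collected and the Week 12 change summaries leave them out

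*Protocol*

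**What the plan says.** **Follow-up after stopping cream.** Protocol 7.1.1: "Participants may choose to discontinue study treatment and remain in the study to be followed for safety/efficacy assessments". Protocol 7.1.2 repeats the option of giving up treatment but "continuing in the follow-up period of the study for safety/efficacy assessments".

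**Diary.** Protocol 8.2.7.1 has both NRS items recorded daily "in the evening beginning on the day of screening through Week 24 or treatment discontinuation". SAP 7.2.5.1 has the same stop for itch, and SAP 7.2.5.2 has it for Skin Pain ("beginning on the day of screening through Week 24 or treatment discontinuation"). Table 3 of the Protocol ends both items at the last application of study drug.

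**Visits.** Table 3, footnote b: "Assessment for ET will be the same as Week 24 visit". That visit takes place when treatment stops. The only scheduled visit after it is the 30-day safety follow-up, for which Table 3 lists neither NRS nor CLISSCO. CLISSCO is not a diary item: "Investigator will be asked to document score of each of the 12 items" (Protocol 8.2.3).

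**Analysis.** SAP 7.4 puts all secondary efficacy analyses on the ITT population. SAP 7.4.1 gives Week 12 summary statistics for Skin Pain and CLISSCO and says that an MMRM may be fitted. For Skin Pain, SAP 7.2.5.2 states: "No imputation will be performed for missing values". SAP 7.2.2 says the same for CLISSCO. For the primary endpoint, the note to Table 10 in Protocol 10.4.1 counts everyone who discontinues treatment before the timepoint as a nonresponder. SAP 7.3.1 names missing Week 12 values but not discontinuation. SAP 7.4.2 admits time-to-ITCH4 measurements up to 30 days after the last application in the double-blind period, or until open-label cream starts if that is earlier.

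**The concern.** The Protocol offers efficacy follow-up that its own schedule does not deliver. A woman who stops at Week 4 and is willing to keep reporting has nothing to report on, and no visit at Week 12.

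Stopping is also likely to be related to outcome. No rescue treatment is allowed (Protocol 6.6.3). Spread beyond 10% BSA, and worsening LS treated with a prohibited medication, both require discontinuation (Protocol 7.1.1). The women missing at Week 12 may therefore include those doing worst.

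Two things are at stake. The Week 12 Skin Pain and CLISSCO summaries carry an ITT label but leave out most women who stopped earlier. And nobody can later compare the assumed nonresponse of discontinuers with what they would have reported, because a daily score that was not collected cannot be recovered.

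**Working it through.** The plan states no power, effect size, SD or dropout rate, so there is no figure to reproduce. Dropout rates and outcome gaps below are assumptions. The sample size of about 60, 1:1 (30 per arm), is from Protocol 10.1.

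**1. Schedule.** Protocol 8.8.1 places the follow-up visit 30 days (+7) after the ET visit. For an ET visit at Week 4 (about day 28), that is day 28 + 30 = 58 to 28 + 37 = 65. Week 12 is about day 84. Follow-up is over before Week 12 and includes no efficacy measure.

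**2. Which Week 12 NRS scores survive.** The visit score is the mean of the 7 daily scores before the visit and is set to missing if 4 or more are missing. If the last entry is *k* days before the visit, 8 − *k* scores remain. With *k* = 4 there are 4 scores and the visit score exists. With *k* = 5 there are 3 and it is missing. This assumes no other missed entries. Only women who stop within about 4 days of the visit keep a Week 12 score.

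**3. Size of the bias, illustration A.** Assume a Skin Pain change of −3.0 (ruxolitinib) and −1.5 (vehicle) in completers and 0 in discontinuers, with discontinuation rates dr and dv. Completers give −3.0 − (−1.5) = −1.5 whatever the rates. All randomised give

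(1 − dr)(−3.0) − (1 − dv)(−1.5) = −1.5 + 3dr − 1.5dv,

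so the two differ by 3dr − 1.5dv.

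| dr | dv | 3dr − 1.5dv | All randomised | Completers |
|---|---|---|---|---|
| 5% | 25% | 0.150 − 0.375 = −0.225 | −1.725 | −1.5 |
| 15% | 15% | 0.450 − 0.225 = +0.225 | −1.275 | −1.5 |
| 5% | 10% | 0.150 − 0.150 = 0 | −1.5 | −1.5 |
| 10% | 20% | 0.300 − 0.300 = 0 | −1.5 | −1.5 |

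Completers understate the effect in the first row, overstate it in the second, and are right whenever vehicle dropout is twice active dropout.

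**4. Illustration B, same gap in both arms.** If discontinuers are g points worse than completers in each arm, the bias in the difference is (dv − dr)g. With dv = 20%, dr = 10% and g = 1, 2 or 3, it is 0.1, 0.2 or 0.3 points. With dv = 30% and dr = 10%, it is 0.2, 0.4 or 0.6. With equal rates it is 0. Excess dropout of poor responders on vehicle shrinks the apparent effect.

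**5. Precision.** With equal discontinuation d in both arms, n = 30(1 − d) per arm. The difference detectable with 80% power at two-sided 0.05 is √(2/n) × (1.960 + 0.842) SD.

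| d | Women at Week 12 | Detectable (SD) |
|---|---|---|
| 0 | 60 | 0.723 |
| 5% | 57 | 0.742 |
| 10% | 54 | 0.762 |
| 20% | 48 | 0.809 |
| 30% | 42 | 0.865 |

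**6. What an MMRM would recover.** A simulation used 200,000 women per arm, four visits, SD 2.5, correlation 0.6 and dropout of 11% to 17%.

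| Dropout depends on | True difference | Observed-case | MMRM |
|---|---|---|---|
| Observed scores | −1.490 | −1.424 | −1.492 |
| The unobserved score | −1.506 | −1.395 | −1.455 |

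The observed-case error is 0.066 and 0.111 points, about 4% and 7% of the effect. The simulation lets discontinuers continue on the same course after they stop. It therefore does not show what an MMRM would do if stopping cream changes the score.

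**The case against.** Much of the case on the other side stands.

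- **Remaining is optional.** A reader might infer that all discontinuers stay for efficacy. Sections 7.1.1 and 7.1.2 only permit it and promise no Week 12 value.
- **The diary does not explain both change endpoints.** CLISSCO is investigator-scored and is taken at ET. Its Week 12 value is lost because no later visit schedules it. The diary is also not the only record of itch and pain, since both are CLISSCO symptom items. It is the only readable source of the NRS scores.
- **The comparison need not be of completers only.** That describes the descriptive summaries. An MMRM would use discontinuers' earlier visits, assuming data are missing at random. But the SAP makes it optional, and the readable text contains no missing-data sensitivity analysis.
- **The primary analysis is not biased by this.** Under Protocol 10.4.1, discontinuation is itself nonresponse, so later scores cannot change the result.
- **The 30-day window in SAP 7.4.2 is not necessarily empty.** Protocol 8.2.7.1 ends the diary at discontinuation, which can come after an interruption of more than 2 weeks (Protocol 6.5.2). Entries can then follow the last application. Under Table 3 they cannot, so those two passages disagree.
- **Later scores may reflect other LS treatment.** Putting them in the main analysis would change what is estimated. These endpoints are also secondary, in a study not sized by a power calculation. This is a good reason to keep such scores in a supplementary analysis, but not a reason to leave them uncollected.

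**Conclusion.** The inconsistency is real. The Protocol allows efficacy follow-up after cream is stopped, yet the diary ends and no efficacy visit follows ET. Week 12 Skin Pain is therefore unobserved for women who stop more than about 4 days before the visit, and Week 12 CLISSCO is unobserved for want of a visit. The ITT-labelled summaries in practice describe women still on cream.

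The size is not known. Under the assumptions of illustration A the error is 3dr − 1.5dv, about 0.2 points in either direction at 5% v 25% or 15% v 15%, and zero when vehicle dropout is twice active dropout. A reader might take 0.225/1.5 = 15% as the bias to expect. The documents do not support that, because it follows from one choice of rates and from assuming no change at all in discontinuers. The primary ITCH4 result stands as planned. What is lost there is the means to check its nonresponder rule against observed scores.

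**What to change.** **Protocol 8.2.7.1 and Table 3.** Continue the itch and pain diary to the scheduled Week 12 date for women who stop cream before Week 12 and have not withdrawn consent. Record CLISSCO at Week 12 if they attend. State one diary end in both places.

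**SAP 7.4.1.** Commit to the MMRM for change in Skin Pain and CLISSCO. Add supplementary Week 12 analyses of Skin Pain, CLISSCO and ITCH4 that use observed scores regardless of discontinuation, with scores taken under other LS treatment flagged.

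**SAP 7.3.1.** Restate the rule of Protocol 10.4.1 that treatment discontinuers are nonresponders. Without it, newly collected scores could turn a discontinuer into a responder in the primary analysis.

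**SAP 7.4.2.** Reconcile the 30-day window with the diary end.

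If the sponsor does not want this follow-up, the minimum is to remove the mention of efficacy from Protocol 7.1.1 and 7.1.2.

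**Cost.** A short amendment and some SAP wording. The women already have the diary. The downside is a small diary burden on a few women, and some scores taken under other treatment.
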